## 6.5. Study Drug Compliance

For participants in the safety population, overall compliance (%) for INCB050465 will be calculated for all participants as

$$\text{compliance (\%)} = 100 \times [\text{total dose actually taken}] / [\text{total prescribed dose}].$$

The total prescribed dose is defined as the sum of the doses prescribed by the investigator accounting for dose modifications.

The total actual dose taken will be calculated based on information entered on the drug accountability CRF. If there are dispensed drugs that have not been returned yet, the actual dose taken starting from the dispense date of the unreturned drugs will be imputed by the dose taken as reported on the dosing CRF.

## 6.6. Prior and Concomitant Medication

Prior medications and concomitant medications will be coded using the WHO Drug Dictionary. Number and percentage of participants in the FAS with each prior and concomitant medication will be summarized by WHO drug class and WHO drug PT.

## 7. EFFICACY

[Appendix A](#) provides a list of planned tables, figures, and listings. Sample data displays are included in a separate document.

### 7.1. Efficacy Hypotheses

Not applicable.

### 7.2. Response Assessment

An objective assessment of disease status is required at baseline (screening) using the CT-based response criteria of the Lugano Classification ([Cheson et al 2014](#)). Disease status will be subsequently assessed by CT/MRI every 8 weeks through Week 24, then every 12 weeks through Week 96, and then every 24 weeks thereafter until disease progression.

Bone marrow examination is required at baseline assessment at screening except for reasons provided in Section 7.6.2 of the Protocol. If disease is present in bone marrow at baseline, a bone marrow examination will be required to confirm CR or may be performed as clinically indicated. If the bone marrow does not have lymphoma involvement at baseline, a repeat marrow examination is not required to confirm indication of CR on imaging. For participants with splenic MZL without measurable disease (ie, only have histologically confirmed bone marrow infiltration), a bone marrow biopsy/examination must be performed when the number of lymphocytes in the blood normalize.

Sites will use the CT-based response criteria of the Lugano Classification ([Cheson et al 2014](#)) to assess response to treatment locally. At each postbaseline disease assessment, response will be collected in the eCRF as CR, PR, SD, PD, or NE.

All imaging will be submitted to an IRC. Imaging data and applicable clinical data will be reviewed and response assessed using the CT-based response criteria of the Lugano Classification ([Cheson et al 2014](#)) by independent reviewers as described in the Independent Review Charter. An overall timepoint response at each postbaseline disease assessment, the best overall response, the date of initial response (if applicable), and the date of disease progression along with reason(s) of disease progression (if applicable) for each participant, considering radiographic data and clinical data, will be provided by the clinical reviewer. Data as determined by the IRC will be used in the analyses of related efficacy endpoints for all participants and participants who have at least 2 prior therapies in the FAS.

### **7.3. Analysis of the Primary Efficacy Parameter**

The primary efficacy analyses will be conducted when all participants in the FAS who have achieved a response (ie, CR or PR) as determined by IRC have been followed approximately 12 months from the onset of first response.

#### **7.3.1. Best Overall Response and Objective Response Rate**

For responses as determined by IRC, the best overall response for each participant will be provided by the clinical reviewer. A participant is considered an objective responder if they have a best overall response of CR or PR.

The ORR is the proportion of objective responders. Participants who do not have sufficient baseline or on-study response assessment information to be adequately assessed for response status will be included in the denominators in the calculation of ORR.

Best overall response as determined by IRC will be summarized descriptively. The ORR as determined by IRC with 95% CIs will be calculated. Confidence intervals will be calculated based on the exact method for binomial distributions.

Because participants who switched to the selected treatment regimen after starting the maintenance dose received a mixture of the non-selected and selected maintenance regimens and could confound the efficacy evaluation of the non-selected treatment regimen, a sensitivity analysis of ORR as determined by IRC will be provided to summarize these crossover participants as a separate treatment regimen. In addition, the number of participants who achieved best overall response as determined by IRC after the time of crossover along with the best overall response data will be presented under this separate treatment regimen. The analyses described above will be summarized for all participants and participants who have at least 2 prior therapies in the FAS.

When applicable, sensitivity analysis of ORR as determined by an IRC may be provided excluding participants that do not have evaluable radiological images at baseline per the IRC.

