3.1. Subject Inclusion Criteria

A subject who meets all of the following criteria may be included in the study:

1. Men and women, aged 18 or older (except in South Korea, aged 19 or older).
2. Histologically confirmed MZL, including extranodal, nodal, and splenic subtypes.
3. Previously received 1 or more lines of systemic therapy, including at least 1 anti-CD20 antibody (either as monotherapy or in combination as chemoimmunotherapy), with documented progression or documented failure to achieve CR or PR after the most recent systemic treatment regimen.
 - a. Subjects in Cohort 1 must have received prior ibrutinib (**NOTE:** Cohort 1 will be closed to further enrollment with Protocol Amendment [Version] 3).
 - b. Subjects in Cohort 2 must not have received a prior BTK inhibitor (eg, ibrutinib).
 - c. Subjects with *H. pylori*-positive gastric extranodal MZL who received an initial treatment with currently accepted antibiotics may be considered eligible if, after antibiotic regimen, subject has histologically confirmed MZL and was subsequently treated with at least 1 line of systemic therapy.

4. Radiographically measurable lymphadenopathy or extranodal lymphoid malignancy (defined as the presence of ≥ 1 lesion that measures > 1.5 cm in the LDi and ≥ 1.0 cm in the longest perpendicular diameter as assessed by CT or MRI per response criteria for lymphomas ([Cheson et al 2014](#))).
 - a. Subjects with splenic MZL who do not meet the radiographically measurable disease criteria described herein are eligible for participation provided that bone marrow infiltration of MZL is histologically confirmed.
5. Subjects must be willing to undergo an incisional or excisional lymph node or tissue biopsy or provide a lymph node or tissue biopsy from the most recent available archival tissue.
 - a. Subjects with splenic MZL who do not have a tumor to biopsy or an archival tumor tissue sample are eligible for participation provided subject is willing to undergo a bone marrow biopsy or provide an archival bone marrow biopsy that was obtained since completion of last therapy and within 2 years before the date of the first dose of study treatment; bone marrow sample must show histologically confirmed infiltration of MZL.
6. Life expectancy > 3 months.
7. ECOG performance status 0 to 2 ([Oken et al 1982](#); see [Appendix B](#)).
8. Adequate hematologic, hepatic, and renal function (values must not be achieved with growth factors):
 - a. ANC $\geq 1.0 \times 10^9/L$.

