5.6.2. Restricted Medications

- Use of systemic corticosteroid doses ≤ 10 mg/day prednisone (or equivalent) is permitted but discouraged from the screening visit through EOT.
- Short courses of systemic corticosteroid doses > 10 mg/day prednisolone or equivalent are permitted only in the case of severe or life-threatening complications, which cannot be controlled with other drugs, but are otherwise discouraged from the screening visit through EOT.
- Use of weak or moderate inducers or inhibitors of CYP3A4 (see Appendix D) is discouraged, and investigators should seek other options where possible.

- Use of P-glycoprotein substrates of clinical relevance should be used with caution (ie, aliskiren, ambrisentan, colchicine, dabigatran etexilate, digoxin, everolimus, fexofenadine, imatinib, lapatinib, maraviroc, nilotinib, posaconazole, ranolazine, saxagliptin, sirolimus, sitagliptin, talinolol, tolvaptan, topotecan) from the screening visit through the EOT visit.
- Localized radiotherapy will be permitted if administered as treatment for pain or impending compression fractures and with prior approval of the medical monitor.

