Description of change: Clarified language on how PJP prophylactic agents will be supplied.

Rationale for change: Incyte will not provide PJP prophylactic agents, but rather sites will be responsible for sourcing from commercial supply and Incyte will reimburse.

5. Section 5.5.1, Criteria for Study Treatment Discontinuation

Description of change: The following bullet has been deleted from Section 5.5.1: If a subject is found not to have met eligibility criteria, then the medical monitor and investigator will collaborate to determine whether the subject should be withdrawn from the study.

Rationale for change: Requested by US and Canadian regulatory authorities during review of other Incyte protocols.

6. **Section 5.6.2, Restricted Medications; Section 5.6.3, Prohibited Medications**

[figure not shown]
Description of change: Radiation therapy was removed from Section 5.6.3 as it was redundant with Section 3.2 (Exclusion Criterion 10), which lists excluded, concurrent anticancer therapies. A description of permitted radiotherapy was added to Section 5.6.2.

Rationale for change: Administration of localized radiotherapy in cases of pain or impending compression fractures may be permitted to allow subjects who are otherwise benefitting to continue study treatment.

7. **Section 5.6.3, Prohibited Medications**

Description of change: A statement was added noting that exposure to a live vaccine is prohibited within 30 days of study treatment through 3 months after the last dose of INCB050465.

Rationale for change: Requested by MHRA.

9. **Synopsis; Section 3.1, Subject Inclusion Criteria; Section 6, Study Assessment (Table 5, Schedule of Assessments); Section 7.8.5, Tumor**

Description of change: Language was added to allow subjects with splenic MZL to participate if a bone marrow biopsy is provided at baseline.

Rationale for change: Subjects with splenic MZL may not have a tumor lesion to biopsy or an archival tumor tissue to provide. Therefore, a bone marrow sample histologically confirming infiltration of MZL is allowed.

10. **Appendix A, Information Regarding Effectiveness of Contraceptive Methods**

Description of change: Provided information for male contraception methods.

Rationale for change: Informational.

12. **Incorporation of administrative changes.** Other minor, administrative changes have been incorporated throughout the Protocol and are noted in the redline version of the amendment.

Amendment 1-FRA (23 FEB 2018)

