#### **7.4.5. Best Percentage Change in Disease Burden**

For each participant with measurable lesions at baseline, target lesion size as measured by sum of product of diameters of all target lesions will be used as the measure for disease burden. For all participants and participants who have at least 2 prior therapies in the FAS, the best percentage change from baseline, defined as the largest decrease in target lesion sizes during the study, will be summarized, and a waterfall plot of the best percentage change will be generated using data from IRC. Note that for participants who only have increases in target lesion sizes from baseline, the smallest increase will be considered as the best change from baseline. For IRC, there will be 2 radiologic reviewers for each participant. An adjudication will be performed per the Independent Review Charter when Reviewers 1 and 2 disagree on the CT/MRI best overall response, or when best overall response is consistent and the date of initial response and/or the date of PD differ between Reviewers 1 and 2. The adjudicator will choose the read that he or she believes most accurately represents the adjudication parameter(s) in question. This is considered the "accepted read," and data from this reviewer will be used for the analysis. When there was no adjudication needed, data from Reviewer 1 will be used for the analysis. An indicator is provided to identify the read that is considered to be the accepted assessment in data from IRC.

[figure not shown]
For splenic MZL participants who have splenomegaly only at baseline, the spleen size as measured by the enlarged portion of the splenic length (ie, splenic length in excess of the 13 cm normal threshold) will be used as the measure for disease burden. The best percentage change from baseline, defined as the largest decrease in spleen size during the study, will be summarized, and the best percentage change using data from IRC will be included in the waterfall plot as described above. Note that for participants who only have increases in spleen size from baseline, the smallest increase will be considered as the best change from baseline.

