Best change in disease burden as reported by the investigator will also be summarized as described above for all participants in the FAS. Target lesions considered "too small to measure" will be assigned a default value of 5 mm × 5 mm for purposes of this analysis. Likewise, target lesions identified as "not present" at postbaseline assessments will be assigned 0 mm × 0 mm for this analysis. In the event a target lesion is unaccounted for in a particular postbaseline timepoint (ie, assessment missing or NE), then the overall sum of product of diameters for target lesions will not be evaluable for that postbaseline timepoint.

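### Best percentage change and the investigator response rates have no cut-off at permitted radiotherapy to a target lesion or at new anticancer treatment, so shrinkage from either counts as drug effect

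*SAP*

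**What the plan says.** **Radiotherapy.** Protocol 5.6.2: "Localized radiotherapy will be permitted if administered as treatment for pain or impending compression fractures and with prior approval of the medical monitor". The section does not say which lesions may be irradiated. The amendment rationale in Protocol Appendix E explains that the allowance "may be permitted to allow subjects who are otherwise benefitting to continue study treatment". Such a participant stays on drug, and the CT/MRI schedule continues.

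**Measurable disease.** Protocol 3.1, criterion 4, asks for measurable disease "defined as the presence of ≥ 1 lesion that measures > 1.5 cm in the LDi" (with a perpendicular-diameter limit), so one target lesion is enough.

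**Best percentage change.** SAP 7.4.5 defines it as the best change from baseline, "defined as the largest decrease in target lesion sizes during the study". The IRC version takes its measurements from the accepted radiologic read: "data from this reviewer will be used for the analysis". The lesion rules given there for investigator data cover lesions that are too small to measure, no longer present, or missing or not evaluable. For participants with splenic MZL who have only splenomegaly at baseline, splenic length above 13 cm replaces the target sum.

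**Investigator response.** SAP 7.2: "Sites will use the CT-based response criteria of the Lugano Classification". Protocol Appendix C requires, for partial remission, a fall of at least 50% in the summed products of up to 6 target lesions, and has no provision for an irradiated lesion. Protocol 9.4.1.3 and SAP Appendix A (Table 2.1.2) provide for investigator ORR and CRR. The responder rule is the one in SAP 7.3.1: "A participant is considered an objective responder if they have a best overall response of CR or PR".

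**New anticancer treatment.** SAP Table 2 censors PFS at the last valid assessment on or before it, and SAP 7.4.1 carries this over to DOR. SAP 7.3.1, 7.4.2 and 7.4.5 have no matching cut-off.

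**The concern.** The trial has no comparator, so once a target lesion has been irradiated, nothing in the data separates the effect of radiation from that of the drug. Protocol 1.2 lists radiation as a treatment for MZL, including low-dose radiation of the spleen, so shrinkage of an irradiated lesion is to be expected.

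Best percentage change is the most exposed result because it takes the largest decrease over the whole study. A participant who was already a responder keeps the same responder status after radiotherapy, but the best change can still deepen and a PR can be read as a CR. The values feed the summary table and the waterfall plot. Investigator ORR and CRR are reported beside the IRC results and would carry the same effect.

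The SAP already accepts the principle elsewhere. Table 2 stops PFS and DOR at new anticancer treatment, and the crossover sensitivity analyses of DOR and PFS exclude assessments made after the switch. If no cut-off is written down in advance, the choice would be made after the responses are known.

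**Working it through.** The plan gives no figure on this point. Its response-rate probabilities (SAP 3.3 and 10) are not used here: the interim rule in SAP 10 is on IRC response, and SAP 3.3 goes with the primary IRC ORR.

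**Step 1. Effect on one participant's target sum.**
Take m equal target lesions, with the irradiated one going to zero. Its share of the sum is s = 1/m. The fall c that the other lesions need for a 50% fall in the whole sum solves s + (1 − s)c = 0.5, so c = (0.5 − s)/(1 − s).

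| Target lesions m | Share s | Fall needed in the other lesions |
|---|---|---|
| 1 | 100% | no other lesions; a 50% fall in the irradiated one is enough |
| 2 | 50% | 0% |
| 3 | 33.3% | 25.0% |
| 4 | 25% | 33.3% |
| 5 | 20% | 37.5% |
| 6 | 16.7% | 40.0% |

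This concerns the size criterion only. Appendix C also requires, for PR, no new lesions, no increase in non-measured disease, and sufficient regression of an enlarged spleen.

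**Step 2. Example for best percentage change.**
Two equal lesions; the irradiated one disappears and the other falls 30%. The sum falls (100% + 30%)/2 = 65%. SAP 7.4.5 records −65%, while the unirradiated lesion shows −30%. The first value meets the PR size criterion and the second does not.

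**Step 3. Weight in investigator ORR.**
One false responder is worth 1/90 = 1.1 points at n = 90, or 1/60 = 1.7 points at n = 60. The documents give no radiotherapy rate. For an assumed 1 to 5 false responders, the excess is 1.1 to 5.6 points at n = 90 (5/90 = 5.6%). This assumes that every one of them would otherwise have been a non-responder, so it is an upper reading of that range.

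**Step 4. New anticancer treatment.**
Protocol 6.4.2 and 7.6.1 end disease imaging at the start of new therapy, 6.4.1 moves the subject to survival follow-up, and 5.6.3 prohibits other anticancer medication through the 30-day follow-up. Two routes remain: tumor assessments supplied from site records (6.4.3) and unscheduled visits (6.6). This route is narrower than radiotherapy on treatment.

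**Step 5. Table 2 and permitted radiotherapy.**
Exclusion criterion 10 (Protocol 3.2) lists radiation therapy under concurrent anticancer therapy, and the Appendix E rationale refers to it in those terms. Section 5.6.2 nevertheless permits it on study as supportive treatment for a participant who continues the drug. SAP Table 2 does not say which classification governs censoring of PFS and DOR, so two programmers could reasonably differ.

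**The case against.** **The affected group is narrow.** Radiotherapy needs pain or impending compression fracture and prior approval from the medical monitor, and it is meant for participants who are otherwise benefitting, many of whom may already be responders. Radiographic progression ends study treatment (Protocol 5.5.1). A false PR needs a non-responder without progression, irradiated on a target lesion, who also meets the other Appendix C criteria. This stands, and it is why the likely effect is small.

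**The results concerned are descriptive or supportive.** That also stands. It lowers the stakes but does not make the recorded values right.

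**A reader might infer that the primary IRC ORR is inflated.** The documents do not support this. SAP 7.2 has the IRC clinical reviewer assign best overall response from radiographic and clinical data under the Independent Review Charter. The charter is not among the documents and may well deal with irradiated lesions. The same caution applies in part to IRC best change: the SAP fixes the calculation, but the charter governs the reads.

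**A reader might infer that permitted radiotherapy plainly falls outside new anticancer treatment.** The eligibility text classes radiation as anticancer therapy, so neither answer can be assumed.

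**A reader might infer that the missing-lesion rule in SAP 7.4.5 would cost a participant a response.** That rule says "then the overall sum of product of diameters for target lesions will not be evaluable for that postbaseline timepoint". It belongs to the best-change calculation and does not decide CR or PR. A measured irradiated lesion is also neither missing nor not evaluable.

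**Conclusion.** The point holds for best percentage change (SAP 7.4.5) and for investigator ORR and CRR. Followed as written, these rules credit the drug with shrinkage of an irradiated target lesion, and with any shrinkage recorded after new anticancer treatment. For one participant the distortion can be large: 65% against 30% in the example, and the entire change when there is a single target lesion. For the trial it is probably small. The number affected is unknown, and each false responder moves investigator ORR by 1.1 points at n = 90.

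No effect on the primary IRC ORR or on the IRC CRR has been shown. The conclusion rests on two assumptions: that no redacted text or separate site instruction already sets a rule, and that at least one target lesion, or a spleen used as the disease-burden measure, is irradiated or assessed after new treatment. If neither happens, the cut-off changes nothing.

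**What to change.** 1. In SAP 7.4.5, and for investigator best overall response (ORR and CRR), state that only assessments on or before the earlier of (a) the start of new anticancer treatment and (b) the first radiotherapy to a target lesion count toward CR, PR and best percentage change. Where splenic length is the disease-burden measure, radiotherapy to the spleen replaces (b). Participants without CR or PR by then are non-responders.
2. In SAP Table 2, state whether radiotherapy permitted under Protocol 5.6.2 is new anticancer treatment for PFS and DOR. Either answer can be defended; one must be written down.
3. Confirm that the Independent Review Charter applies the same cut-off to IRC response.

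**Cost.** SAP wording and one derivation flag. Protocol 7.4 already has procedures recorded in the eCRF up to the end of study treatment, but irradiated sites must be matched to target lesions.

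The statistical price is that a genuine later drug response is not counted once a target lesion has been irradiated. With two equal lesions, one irradiated and gone and the other later down 55%, the unirradiated lesion alone passes 50%, yet the participant stays a non-responder. Reported response may therefore fall slightly. Re-deriving response from the non-irradiated lesions would keep such cases, but it departs from Appendix C and could require charter changes and re-reads. The simple cut-off is the more proportionate choice.
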